### **9.3.1 Blinding**

This is a double-blinded trial in which LEO 138559 and placebo are visually distinct from each other and not matched for viscosity. Neither the subject nor any of the investigators or LEO Pharma staff (except unblinded CRAs) who are involved in the clinical evaluation and monitoring of the subjects will be aware of the treatment received.

IMP will be prepared, handled, and administered by a qualified, unblinded HCP at the site who will not be involved in the management of trial subjects and who will not perform any of the assessments.

In the event that the treatment allocation for a subject becomes known to the investigator or other trial staff involved in the management of trial subjects, LEO Pharma must be notified immediately.

Should an issue arise with the IMP (e.g., damaged kit or syringe that has been assigned to a subject prior to administration, or any other unexpected event with the kit or syringe [e.g. a malfunction during IMP administration]), the unblinded HCP at the site will contact the unblinded CRA to determine whether any specific actions are required.

The trial site will maintain a written plan (site blinding plan) detailing which staff members are blinded/unblinded and the process of IMP administration used to maintain the blind.

### **9.3.2 Emergency unblinding of individual subject treatment**

While the safety of a subject always comes first, it is still important to carefully consider if unblinding is necessary to ensure a subject’s safety. An emergency unblinding request can be made by the investigators, HCPs who are not members of the trial staff, or authorised LEO Pharma personnel.

Provisions are in place for 24-hour emergency unblinding of individual subject treatment. If emergency unblinding is required, the investigator can unblind a subject’s treatment in the

THIS DOCUMENT CONTAINS CONFIDENTIAL INFORMATION AND MUST NOT BE COPIED OR MADE AVAILABLE TO ANY THIRD PARTY WITHOUT THE PRIOR WRITTEN CONSENT OF THE LEO PHARMA GROUP

IRT. For a requester who is not a member of the trial staff and who does not have access to the IRT (e.g., a physician at an emergency room), a local contact number for the emergency unblinding CRO is provided on the subject card (see [Appendix 3B](#)) to be used if the investigator or delegated site staff cannot be reached. The requester will provide the trial ID and subject ID to the emergency unblinding CRO who will immediately reveal the individual treatment allocation.

The emergency unblinding CRO will clarify that the requester requires immediate unblinding without further medical consultation. Should the requester wish to discuss whether unblinding is necessary, the emergency unblinding CRO will provide the requester with the LEO Pharma 24/7 contact which will be diverted to the medical cover.

LEO Pharma Global Safety may unblind subject(s) if it is deemed necessary, including for regulatory purposes in relation to reporting of SUSARs.

## 9.4 Background treatment (emollients)

All subjects must use an emollient twice daily (or more frequently, if needed) for at least 7 days before Day 1 (baseline) and throughout the treatment period (until Week 16). Subjects should use the same emollient throughout the trial.

The emollient should preferably not contain additives such as ceramide, hyaluronic acid, or urea. To ensure use of a suitable emollient, the investigator should provide guidance to the subject as to which locally available emollient to use.

The function of the emollient is to:

- Keep the subject's skin well moisturised in the absence of systemic and/or topical AD treatment(s) in the washout period (Week -1 to Week 0).
- Act as a complement to systemic treatment with the IMP (standard of care) and keep the subject's skin well moisturised in the treatment period (Week 0 to Week 16).

### Reporting in eCRF

It will be recorded in the eCRF if background treatment (emollient) has been used daily; if not, a reason should be provided.

## 9.5 Rescue treatment

If medically necessary (i.e., due to worsening of AD or intolerable AD symptoms), rescue treatment for AD in the form of TCS/TCI may be prescribed to trial subjects and used from Week 4 at the discretion of the investigator. It is recommended that the investigator starts with

THIS DOCUMENT CONTAINS CONFIDENTIAL INFORMATION AND MUST NOT BE COPIED OR MADE AVAILABLE TO ANY THIRD PARTY WITHOUT THE PRIOR WRITTEN CONSENT OF THE LEO PHARMA GROUP

a TCI or least potent TCS for the face (e.g., hydrocortisone 2.5% cream/ointment) and moderately potent TCS for the body (e.g., triamcinolone acetonide 0.1% cream/ointment).

If rescue treatment with TCS/TCI is initiated after Week 4, the subject will continue treatment and the schedule of trial visits and assessments. However, treatment with IMP will be discontinued if a subject receives the following treatment:

- Rescue treatment with any TCS/TCI before Week 4.
- Super potent TCS (e.g., clobetasol propionate 0.05% cream) between Week -1 and Week 16.
- Systemic rescue treatment (besides systemic antihistamines and/or anti-infectives) at any point during the trial between Week -4 (or from 5 half-lives of Week 0, whichever is longer) and Week 16.

Investigators should make every attempt to conduct efficacy and safety assessments (for example disease severity scores, safety labs) immediately before administering any rescue treatment. An unscheduled visit may be used for this purpose, if necessary.

During the safety follow-up period (Weeks 16 to 32), topical therapy (including TCS and TCI) may be prescribed to control disease activity at the discretion of the investigator and will not be considered as rescue treatment. Any medication taken by the subjects during the follow-up period will be reported as concomitant medication using the eCRF.

### Reporting in eCRF

It will be recorded in the eCRF if and what rescue treatment has been used.

## 9.6 Concomitant medication and concurrent procedures

Any medication or vaccine that the subject receives from 3 months prior to screening through to safety follow-up must be recorded in the subject's medical record and the eCRF along with details such as:

- Medication name or therapy (generic or brand name).
- Whether the medication or therapy is a rescue treatment for AD.
- Indication.
- Start and stop date of administration (it will also be recorded if the medication is ongoing).
- Dosage information, including dose per administration, unit, and frequency.

THIS DOCUMENT CONTAINS CONFIDENTIAL INFORMATION AND MUST NOT BE COPIED OR MADE AVAILABLE TO ANY THIRD PARTY WITHOUT THE PRIOR WRITTEN CONSENT OF THE LEO PHARMA GROUP

- Route of administration: oral, topical, SC, transdermal, intraocular, intramuscular, respiratory (inhalation), intralesional, intraperitoneal, nasal, vaginal, rectal, IV, or other (if other, a specification must be provided).

For topical treatments, the dosage form (cream, lotion, ointment, other) and the potency will also be recorded.

For topical, SC, transdermal, intramuscular, and intralesional treatments, the location of administration including laterality will also be recorded (e.g., left upper arm).

Similarly, any concurrent procedure conducted within 3 months prior to screening must also be recorded in the subject's medical record and the eCRF with details such as:

- Procedure name.
- Body location (upper limb, lower limb, trunk, head).
- Indication.
- Start and stop date (it will also be recorded if the procedure is ongoing).

It should be included whether the procedure is inside the area of injection or the area of an AD lesion.

Investigators may prescribe concomitant medications or treatments to provide adequate supportive care as deemed necessary, except for medications listed in Section 9.7. The sponsor's medical expert should be contacted if there are any questions regarding concomitant or prior therapy.

The following concomitant medications are permitted during the trial:

- Paracetamol use (maximum 2 g/day).
- Concomitant therapies taken for the long-term treatment of pre-existing conditions can continue during the trial provided they are in accordance with the exclusion criteria (see Section 8.3).
- Systemic antihistamines and/or anti-infectives.
- Emollients allowed during the treatment period.

For AD patients with mild chronic asthma (42) or mild allergic rhinitis, use of inhaled corticosteroids up to and including 500 µg beclometasone (or equivalent) per day is acceptable.

THIS DOCUMENT CONTAINS CONFIDENTIAL INFORMATION AND MUST NOT BE COPIED OR MADE AVAILABLE TO ANY THIRD PARTY WITHOUT THE PRIOR WRITTEN CONSENT OF THE LEO PHARMA GROUP

## 9.7 Prohibited medication and procedures

Prohibited medications and/or procedures are listed in [Panel 5](#). Details regarding prohibited medications and/or procedures prior to screening and during washout(s) are described in Section [8.3](#).

If prohibited medications are used during the trial, they must be recorded as concomitant medication in the eCRF (Section [9.6](#)).

### Panel 5: Prohibited medication(s) and/or procedure(s)

Medication or procedure	Prohibited from	Prohibited to
TCS or TCI (other than those permitted as rescue treatment).	Washout (Week -1).	Week 16.
Topical PDE-4 inhibitors.	Washout (Week -1).	Week 16.
Other topical prescription medications or prescription emollients/moisturisers (other than the ones allowed during treatment period) used for the treatment of AD.	Washout (Week -1).	Week 16.
Use of UVA, UVB, PUVA, other phototherapy, or tanning beds.	Week -4 prior to randomisation.	Week 16.
Immunoglobulin or blood products.	Week -4 or 5 half-lives prior to randomisation, whichever is longer.	Safety follow-up (Week 32).
Systemic corticosteroids (excluding inhaled or intra-nasal steroids).	Week -4 prior to randomisation.	Safety follow-up (Week 32).
Systemic immunosuppressive/immuno-modulating medication (excluding systemic antihistamines).	Week -4 or 5 half-lives prior to randomisation, whichever is longer.	Safety follow-up (Week 32).
Biologics.	Week -16 or 5 half-lives prior to randomisation, whichever is longer.	Safety follow-up (Week 32).
Allergen immunotherapy.	Week -4 prior to randomisation.	Safety follow-up (Week 32).
Live (attenuated) vaccine.	Week -12 prior to randomisation.	Safety follow-up (Week 32).

**Abbreviations:** AD = atopic dermatitis; PDE-4 = phosphodiesterase-4; PUVA = psoralen ultraviolet A; TCI = topical calcineurin inhibitor(s); TCS = topical corticosteroid(s); UVA = ultraviolet A; UVB = ultraviolet B.

The sponsor's medical expert must be notified if a subject receives any of these prohibited medications during the trial.

THIS DOCUMENT CONTAINS CONFIDENTIAL INFORMATION AND MUST NOT BE COPIED OR MADE AVAILABLE TO ANY THIRD PARTY WITHOUT THE PRIOR WRITTEN CONSENT OF THE LEO PHARMA GROUP

As described in Section 9.5, TCI and TCS used as rescue treatment for worsening of AD or intolerable AD symptoms are allowed from Week 4.

## 9.8 Treatment logistics and accountability

### 9.8.1 Labelling and packaging of trial products

IMP will be packed open label in individually numbered kits.

Primary and secondary packaging materials (vial and outer carton, respectively) will be individually labelled.

The labelling of IMPs will be in accordance with the EU guidelines for Good Manufacturing Practices for Medicinal Products for Human and Veterinary use, Annex 13 (46), local regulations, and trial requirements. Label text will be translated into local languages as required.

### 9.8.2 Storage of trial products

All LEO Pharma supplied IMPs must be stored in a secure and restricted area under the conditions specified on the label and remain in the original container until dispensed.

The IMP must be stored at 2 to 8°C at the site. The temperature during storage must be monitored by a calibrated, stationary, and continuously monitoring system. Minimum requirement is a calibrated min/max thermometer.

A temperature log must be kept to document the storage within the right temperature interval. Storage facilities should be checked at least every working day.

Storage of IMP may be delegated, e.g., to a hospital pharmacy, as locally applicable.

Note that in the cases listed below, site staff should not use the affected IMP and should immediately contact their unblinded CRA for further guidance:

- Temperature excursion upon receipt or during storage at the trial site.
- Damaged kit upon receipt.
- Damaged vial.

Damaged IMP should be documented via IRT (refer to the IRT quick reference guide for further details). Damaged IMP should not be used.

THIS DOCUMENT CONTAINS CONFIDENTIAL INFORMATION AND MUST NOT BE COPIED OR MADE AVAILABLE TO ANY THIRD PARTY WITHOUT THE PRIOR WRITTEN CONSENT OF THE LEO PHARMA GROUP

### 9.8.3 Drug accountability

The investigator is fully responsible for the IMPs at the trial site and for maintaining adequate control of the IMPs and for documenting all transactions with them.

Dispensing of IMPs may be delegated, e.g., to a hospital pharmacy, as locally applicable.

Documentation of drug accountability must be kept of the IMPs administered to each individual subject randomised in the trial. This documentation must be available during monitoring visits and will be checked by the unblinded CRA to verify correct dispensing of the IMPs. Drug accountability information will be recorded in the IRT system. The IRT system will also maintain the inventory status of all IMPs at the trial site.

The IMP must be fully accounted for by the unblinded CRA with the help of the unblinded HCP. Accountability must be documented in the trial medication inventory log in the IRT.

For further information about handling of trial product at site, including IMP accountability, and reconciliation, please refer to the trial product handling manual.

### 9.8.4 Treatment compliance

IMP injections will be performed by unblinded site staff who will also keep the accountability records up-to-date. Any non-compliance and the reason for it must be recorded in the eCRF.

#### Reporting in eCRF

The following data will be recorded in the eCRF:

Did the subject comply with the IMP dosing schedule (yes, no); If no, a reason will be given. It will also be recorded how much IMP the subject received (partial dose, no dose, and the total number of IMP applications missed since last visit).

- Primary reason for non-compliance – lack of time, adverse event, other (if other, a specification should be provided).
- Date and time of IMP administration (stated for each of the oo injections).
- Site of IMP injection: For the site (upper leg [thigh], stomach area [abdomen] or in the upper, outer arm) the laterality should be specified (right or left).

### 9.8.5 Trial product destruction

Used IMP (i.e., empty vials) and unused IMP must be returned to the CMO for destruction. Used IMP and unused IMP that is no longer available for dispensation (e.g., expired or

THIS DOCUMENT CONTAINS CONFIDENTIAL INFORMATION AND MUST NOT BE COPIED OR MADE AVAILABLE TO ANY THIRD PARTY WITHOUT THE PRIOR WRITTEN CONSENT OF THE LEO PHARMA GROUP

damaged IMP) can be returned on an ongoing basis throughout the trial. Unused IMP (i.e., IMP that is still available for dispensation) can be returned for destruction after the last dosing visit of the last subject at the site.

Syringes used for administration of IMP can be destroyed at site according to local procedures in compliance with local regulations.

## **9.9 Provision for subject care following trial completion**

In order to ensure appropriate treatment of the subjects after they have completed the trial, the subjects will be treated at the investigator's discretion or referred to other physician(s) according to standard practice.

## **9.10 Reporting product complaints**

Any defects or issues with the IMP (e.g., inadequate labelling) must be reported to Global Safety at LEO Pharma on the trial-specific (paper) complaint form within 3 days of first knowledge.

Critical complaints (defined as any defect or issue that has or potentially could have a serious impact for the subject [e.g., SAE or large particles in the vial]) must be reported to Global Safety, LEO Pharma within 24 hours.

Complaint forms should contain a detailed description of the defect or issue, including whether it led to an AE. (S)AEs which occur due to a defect or issue with the IMP will be reported by the investigator as described in Sections [13.3](#) and [13.4](#).

Refer to the trial product handling manual and the IRT quick reference guide for information on how to update the kit status in the IRT.

During the investigation of the product complaint, the IMP must be stored at labelled conditions unless otherwise instructed; the trial site will be notified whether the IMP needs to be returned for further investigation or may be destroyed.

Global Safety, LEO Pharma contact information for reporting product complaints:

[contact]

E-mail address: [[contact]](mailto:[contact])

THIS DOCUMENT CONTAINS CONFIDENTIAL INFORMATION AND MUST NOT BE COPIED OR MADE AVAILABLE TO ANY THIRD PARTY WITHOUT THE PRIOR WRITTEN CONSENT OF THE LEO PHARMA GROUP

## 10 Discontinuation and withdrawal

### 10.1 General principles

A subject may withdraw from the trial (prior to first dose or during the treatment period) or permanently discontinue trial treatment at any time if the subject, the investigator, or LEO Pharma considers that it is not in the subject's best interest to continue.

A subject who withdraws from the trial is a subject who stops treatment with the IMP and all further protocol defined trial activities. A subject who permanently discontinues IMP is a subject who, although they stop treatment with the IMP, agree to their follow-up as described in Section 10.3. Early termination assessments to be conducted for both events are described in Section 10.3.

Subjects who withdraw from the trial and subjects who permanently discontinue IMP will not be replaced.

If a subject withdraws from the trial, they may request destruction of any samples taken and not tested. The investigator must document this in the subject's medical record and inform LEO Pharma.

### 10.2 Reasons for discontinuation of IMP

#### 10.2.1 Reasons for permanent discontinuation of IMP

Subjects will permanently discontinue IMP in the event of:

- Withdrawal of consent.
- An AE that, in the opinion of the investigator or sponsor's medical expert, contraindicates further dosing.
- Initiation of systemic rescue treatment of AD (besides systemic antihistamines and/or anti-infectives) at any point during the trial between Week 0 and 16, rescue treatment before Week 4, and/or super potent TCS between Week -1 and Week 16.
- Initiation of prohibited medication which cannot be safely replaced by other non-prohibited medications.
- Evidence of pregnancy, or if the subject is noncompliant with the contraception requirements (see Section 8).
- Other reasons, at the discretion of the investigator. If other, a specification should be provided.

THIS DOCUMENT CONTAINS CONFIDENTIAL INFORMATION AND MUST NOT BE COPIED OR MADE AVAILABLE TO ANY THIRD PARTY WITHOUT THE PRIOR WRITTEN CONSENT OF THE LEO PHARMA GROUP

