## 14 Statistical methods

### 14.1 Sample size

At baseline, a total of 52 subjects will be randomised 1:1:

- 26 subjects to LEO 138559 450 mg Q2W.
- 26 subjects to placebo Q2W.

The sample size is determined using t-test for pairwise consideration of 2 treatment groups based on the following assumptions:

Treatment	Expected reduction in EASI (SD)*	Attrition rate
LEO 138559	22.9 (13)	30%
Placebo	7.3 (18)	30%

\*Expected reduction in EASI for LEO 138559 is based on results from an upadacitinib phase 2b trial (28), and for placebo, the expected reduction is based on a dupilumab phase 2b trial (58).

With a significance level of 5%, 18 subjects per treatment group will provide a nominal power of at least 80% to detect a difference between the 2 treatment groups. Assuming a maximum attrition rate of 30%, 26 subjects in each treatment group should be randomised into the trial.

Assuming a screening failure rate of 35%, the planned number of subjects to screen is set to 80.

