## 14.3 Statistical analysis

### 14.3.1 General principles

All significance tests will be two-sided using the 5% significance level. All confidence intervals will be presented with 95% degree of confidence, unless otherwise specified. Efficacy analyses will be based on the FAS, and safety analyses will be based on the safety analysis set. PK analysis will be based on the PK analysis set.

If not mentioned otherwise, endpoints will be summarised descriptively at each visit by treatment. For endpoints evaluated over time, plots will be made to explore the trajectories with time.

An observed cases approach will be used for tabulations of data by visit (that is, involving only those subjects who attended each specific visit). For categorical endpoints, the number of subjects not attending each specific visit will also be provided.

Categorical data will be summarised by treatment group, using the number and percentage of subjects in each category. Continuous data will be summarised using the mean, median, standard deviation (SD), 1st quartile, 3rd quartile, minimum, and maximum values.

Additionally, geometric mean and coefficient of variation (CV) will be provided for the PK endpoint.

In general, for endpoints evaluated as change from baseline and/or where a baseline adjustment is applied, baseline is defined as assessments conducted at the randomisation visit (Visit 3), if not otherwise stated. If the information is not available at the randomisation visit but at the (re)screening visit (Visit 1) then this will be used instead.

All the analyses specified in the protocol will be reviewed in relation to the blinded data actually obtained, and the statistical analysis plan will be finalised before breaking the randomisation code.

Any changes from the statistical analyses planned in this clinical trial protocol will be described and justified in a protocol amendment, the statistical analysis plan, and/or in the CTR, dependent on the type of change.

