## Panel 12: Objective and estimands for primary endpoint

Objective	Estimands					Endpoint
	Estimand type (Primary/Supplementary)	Comparison groups	Interpretation of endpoint	Intercurrent events and strategy	Population level summary	
Primary objective To compare the efficacy of LEO 138559 with placebo in subjects with moderate to severe AD.	Primary	Dose of LEO 138559 450 mg Q2W vs. placebo.	Change in EASI from baseline to Week 16 as if all subjects adhered to the treatment regimen, i.e., they did not permanently discontinue IMP and did not use rescue treatment before Week 16 (Section 14.3.8.1).	Events: Permanent discontinuation of IMP, initiation of rescue treatment Strategy: 'Hypothetical'.	Difference in mean change in EASI from baseline to Week 16.	Primary endpoint Change in EASI score from baseline to Week 16.
	First supplementary		Change in EASI from baseline to Week 16 without intercurrent events (Section 14.3.8.2).	Events: Permanent discontinuation of IMP, initiation of rescue treatment Strategy: 'Composite'.		
	Second supplementary		Change in EASI from baseline to Week 16 without intercurrent events and as if COVID-19 pandemic did not happen (Section 14.3.8.3).	Events: Permanent discontinuation of IMP due to non-pandemic-related factors, permanent discontinuation of IMP due to pandemic-related factors, initiation of rescue treatment Strategy: 'Pandemic-modified composite'.		
	Third supplementary		Change in EASI from baseline to Week 16 regardless of intercurrent events (Section 14.3.8.4).	Events: Permanent discontinuation of IMP, initiation of rescue treatment Strategy: 'Treatment policy'.		

**Abbreviations:** AD = atopic dermatitis; COVID-19 = coronavirus disease 2019; EASI = Eczema Area and Severity Index; IMP = investigational medicinal product; Q2W = every second week.

THIS DOCUMENT CONTAINS CONFIDENTIAL INFORMATION AND MUST NOT BE COPIED OR MADE AVAILABLE TO ANY THIRD PARTY WITHOUT THE PRIOR WRITTEN CONSENT OF THE LEO PHARMA GROUP

The following intercurrent events are considered to affect the interpretation of the estimated treatment effects:

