#### 14.3.8.1 Primary estimand

The primary estimand will use a *hypothetical strategy* which attempts to quantify the effect of treatment, in the hypothetical situation, where one or more intercurrent events do not occur. In this context, an intercurrent event refers to a post-randomisation event that either precludes the existence of or affects the interpretation of the measurements of the endpoint e.g., permanent discontinuation of IMP.

This primary estimand evaluates the treatment difference in change in EASI score from baseline to Week 16 as if all subjects adhered to the treatment regimen, i.e., they did not discontinue IMP permanently and no rescue treatment was made available before Week 16. Data collected after permanent discontinuation of IMP or after initiation of rescue treatment will not be included in the analysis, but will be 'treated as missing' and imputed assuming

THIS DOCUMENT CONTAINS CONFIDENTIAL INFORMATION AND MUST NOT BE COPIED OR MADE AVAILABLE TO ANY THIRD PARTY WITHOUT THE PRIOR WRITTEN CONSENT OF THE LEO PHARMA GROUP

MAR. Similarly, for subjects who experience a pandemic-related intercurrent event prior to Week 16, observed data at Week 16 will be ‘treated as missing’ and imputed assuming MAR.

If data is missing at Week 16 due to a non-pandemic-related intercurrent event, the data will be imputed using MI (100 iterations) assuming MAR within each treatment group and whether the subject has experienced a non-pandemic-related intercurrent event. Within a given treatment group, observed data from subjects not experiencing an intercurrent event will be used to impute missing data for subjects who experience an intercurrent event.

Missing data or data ‘treated as missing’ at Week 16 due to the pandemic will be imputed using MI assuming MAR within treatment group using data from subjects who have not experienced an intercurrent event.

For each of the 100 complete datasets, the change in EASI score from baseline to Week 16 will be analysed using an ANCOVA model adjusted for treatment, region, baseline EASI score, and baseline disease severity. The pooled estimate of the difference in the LS-mean change from baseline, along with the associated 95% CIs and nominal p-values will be presented based on applying Rubin’s rules to the estimates and standard errors from the ANCOVA analysis of the imputed datasets.

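### Panel 5 treatment active on AD that is not flagged as rescue and does not end IMP is not an intercurrent event, so the Week 16 EASI it may have altered is used as observed in the primary analysis

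*Combined protocol and SAP*

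**What the plan says.** **Events.** Panel 12 gives, for the primary estimand, "Events: Permanent discontinuation of IMP, initiation of rescue treatment". Section 14.3.8 splits discontinuation by relation to the pandemic and describes the rescue event only as a subject starting rescue, without reference to Panel 5. Section 14.3.8.1 words the target as "as if all subjects adhered to the treatment regimen", and spells this out as no permanent IMP discontinuation and no rescue before Week 16.

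**Rescue.** Section 9.5 says that "rescue treatment for AD in the form of TCS/TCI may be prescribed to trial subjects" from Week 4. It also names systemic rescue, super potent TCS and rescue before Week 4, each of which ends IMP. Section 9.6 requires each medication entry to state whether it is rescue for AD. Its list of items for procedures has no such field.

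**Prohibited treatment.** Panel 5 bars topical PDE-4 inhibitors, other prescription topicals for AD, systemic corticosteroids, systemic immunosuppressants and biologics. It also lists "Use of UVA, UVB, PUVA, other phototherapy, or tanning beds". Section 10.2.1 ends IMP for "Initiation of prohibited medication which cannot be safely replaced by other non-prohibited medications". Otherwise section 9.7 requires the medication to be recorded and the sponsor's medical expert to be notified.

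**Data use.** For a subject with no intercurrent event, Panel 13 uses the observed Week 16 value under all four estimands. Section 14.3.10 sets non-response for rescue, IMP discontinuation and missing data only.

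**The concern.** The hypothetical estimand is meant to describe the randomised regimen without other AD therapy blurring the comparison. Yet a TCS course flagged as rescue removes a subject's Week 16 EASI, while phototherapy in a subject who stays on IMP leaves it in.

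The protocol itself regards such treatment as able to disturb the endpoint. Appendix 7 justifies exclusion criteria 4 to 6 (systemic immunosuppressants, phototherapy, biologics, prescription topicals) by the need to keep efficacy assessments free of interference. The same reasoning applies after randomisation, but the analysis has no matching rule.

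At stake are the primary difference in mean EASI change and the EASI 50/75/90 and vIGA-AD responder counts. With 26 subjects per arm, one subject is 1/26 = 3.8% of an arm.

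**Working it through.** **1. Which subjects fall through.** Take a Panel 5 treatment with activity on AD, started between Week 0 and Week 16.

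- Super potent TCS: IMP stops whatever the label (9.5, 10.2.1). Already an intercurrent event.
- Systemic treatment given as AD rescue: IMP stops. Already covered.
- Any medication flagged as rescue under 9.6: already an intercurrent event.
- Prohibited medication that cannot be safely replaced: IMP stops. Already covered.
- Phototherapy with IMP continued: the procedure record has no rescue field. Not covered.
- PDE-4 inhibitor or other prescription topical, stopped or replaced and not flagged: not covered.
- Systemic corticosteroid or immunosuppressant for another indication, stopped or replaced: not covered.

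The last three groups land in Panel 13's row for no intercurrent event with data observed, and the value is used.

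**2. Whether another analysis catches them.** The MMRM sensitivity analysis (14.3.8.1.1) and the WOCF analysis (14.3.8.2.1) add no rule for prohibited treatment. The responder rule in 14.3.10 and the MMRM for patient-reported outcomes in 14.3.11 name the same two events. Section 14.3.3 sets data aside when more than one dose is missed, which concerns exposure to IMP, not added therapy.

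**3. The plan's own power.** Inputs from section 14.1: expected EASI reductions 22.9 (SD 13) and 7.3 (SD 18), and "With a significance level of 5%, 18 subjects per treatment group will provide a nominal power of at least 80" per cent. From 14.3.1: "All significance tests will be two-sided using the 5% significance level".

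- Effect: 22.9 − 7.3 = 15.6.
- Standard error at 18 per arm: √((13² + 18²)/18) = √(493/18) = 5.23.
- Welch df: 17 × 493² / (169² + 324²) = 30.9.
- Noncentrality: 15.6/5.23 = 2.98; power from the noncentral t = 82.3%.
- At 17 per arm, power is 79.96%, so 18 is the smallest number that reaches 80%.
- 18/0.70 = 25.7, rounded up to 26 per arm, which agrees with "At baseline, a total of 52 subjects will be randomised 1:1".

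The stated figures reproduce.

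**4. Illustration of size.** The documents give no rate of such use and no size of benefit, so both are assumptions here. If shares f(P) on placebo and f(A) on active are affected and each gains g EASI points, the difference changes by −g × (f(P) − f(A)). Below, f(A) = 0 and the SDs are held fixed.

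| f(P) | g | Shift | Effect | Power, 18 per arm |
|---|---|---|---|---|
| none | – | 0 | 15.6 | 82.3% |
| 1/26 | 5 | 0.19 | 15.4 | 81.4% |
| 1/26 | 10 | 0.38 | 15.2 | 80.4% |
| 1/26 | 15.6 | 0.60 | 15.0 | 79.3% |
| 5% | 10 | 0.50 | 15.1 | 79.8% |
| 10% | 10 | 1.00 | 14.6 | 77.1% |
| 15% | 10 | 1.50 | 14.1 | 74.2% |

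If f(P) = f(A) with equal benefit, the shift is zero. If use is higher on active, the sign reverses and the effect is inflated.

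**The case against.** **The text is consistent with itself.** Section 14.3.8.1 defines adherence by exactly two events, and Panels 12 and 13 agree. This stands: the fault is an estimand narrower than the regimen and its prohibited-treatment rules, not a contradiction.

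**Rescue already reaches further than it seems.** A reader might infer from section 9.5 that rescue means TCS or TCI only, so that every other AD treatment escapes. The documents do not support that. The event in 14.3.8 is not limited to TCS or TCI, section 9.6 lets any medication be flagged, and systemic AD rescue and super potent TCS already end IMP. What remains is the narrower set in the first working step.

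**Direction and size.** A reader might infer a bias towards no difference, because placebo subjects have more reason to seek help, and a clear loss of power. The first argument concerns treatment sought for AD, which for medications the rescue flag can capture. It gives no reason for a placebo excess of steroid courses for other conditions. On size, a 10-point benefit exceeds the whole assumed placebo reduction of 7.3, and 15% of 26 is about four placebo subjects (0.15 × 26 = 3.9), all unflagged and all still on IMP. The lower rows of the table are therefore not predictions.

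**Safeguards exist.** The investigator may end IMP for other reasons (10.2.1). Data exclusions are documented before the code is broken (14.2), analyses are reviewed against blinded data (14.3.1), and major deviations are reported (Appendix 3D). All help, but none says how this case is to be analysed.

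**Conclusion.** The gap is real and narrow. It concerns AD-active Panel 5 treatment begun between Week 0 and Week 16, not flagged as rescue, in a subject who continues IMP. For that subject the plan's stated rule keeps the observed Week 16 EASI in the primary analysis and allows responder status. This follows from reading the sections together and does not depend on any calculation.

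Size and direction cannot be known from the documents. The illustration of one placebo subject in 26 with a 10-point benefit costs 0.4 EASI points and 1.9 percentage points of power (82.3% to 80.4%), leaving the stated 80% intact. It assumes no affected subject on active and unchanged SDs. The finding should not be read as showing that the trial is underpowered or that the effect will be understated. It is worth settling before the code is broken because a choice made afterwards could be influenced by the results.

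**What to change.** In section 14.3.8 and Panels 12 and 13, widen the rescue event to, for example: *initiation, between Week 0 and Week 16, of rescue treatment, or of any Panel 5 medication or procedure judged in blinded review able to affect EASI at Week 16, whatever its indication and whether or not it was flagged as rescue.*

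- Base the review on the recorded concomitant medications and procedures, and complete it before the code is broken.
- Write the criteria on timing and duration in advance, so that brief early use that has washed out need not void Week 16. The protocol itself accepts one week off topical treatment before baseline (exclusion criterion 6).
- Handle the event like rescue in the hypothetical estimand and both composite estimands, and as non-response in 14.3.10. Under treatment policy, observed data remain in use.
- Confirm that procedures are captured during treatment. Section 9.6 mentions only the 3 months before screening, whereas Panel 2, footnote o, runs to Week 32.

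The cost is SAP wording, one blinded review of data already collected and possibly a few more imputed Week 16 values. No rule on the clinical use of these treatments changes.
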